1.0 INTRODUCTION

This clinical study protocol defines the MitraClip XTR PMCF study being conducted to confirm the safety and performance of the MitraClip XTR in a post-market setting. The MitraClip XTR System introduces a new delivery catheter design intended to make procedure easier, more precise, more predictable, and to optimize manufacturability and an additional implant size intended to assist clinicians with leaflet grasping. Although there is extensive published clinical evidence on the safety and performance of the MitraClip system (see section 2.1), the safety and performance of the MitraClip XTR system has not yet been evaluated in a clinical study.

This PMCF study will be conducted on commercial MitraClip XTR devices that have received CE Mark and will be used to fulfill the regulatory requirement for post-market clinical follow-up (PMCF).

1.1 Study Design

This is a Post-Market, Multi-Center, International, Single-Arm, Prospective Study to assess the safety and performance of the next generation MitraClip XTR System by comparing the rate of acute procedural success after treatment with the MitraClip XTR to an expected rate based on historical MitraClip data.

A minimum of 220 post-market, consecutive, consented, patients treated with the MitraClip XTR device in the EU will be included for analysis into the MitraClip XTR PMCF study. Clinical follow-up visits will be requested at 30 days and at 12 months post-procedure with an additional clinical follow-up phone call at 6 months. Reported adverse events through 12 months will be assessed to further confirm safety.

1.2 Study Objective

The primary objective of this study is to assess the safety and performance of the MitraClip XTR System in a post-market setting. This study will be conducted in accordance with post market clinical follow-up requirements.

2.0 BACKGROUND INFORMATION

2.1 Literature Review

The MitraClip System received approval for commercialization in Europe in March 2008, and is indicated for reconstruction of the insufficient mitral valve through tissue approximation. Since approval, there have been a number of commercial studies in Europe on the MitraClip.

ACCESS-EU²⁹ was a two-phase prospective, single-arm, multicenter post-approval observational study of the MitraClip in Europe for the treatment of MR. The primary objective was to gain information with respect to health economics and clinical care, and to provide further evidence of safety and effectiveness. Five hundred sixty-seven (567) patients were treated with the MitraClip. One-year clinical follow-up was available in 487 patients. Considering the high MitraClip device implant rate (99.6%, 565/567), the high rate of meaningful MR reduction (78.9%, 258/327 MR<2+), and the resulting improvements in 6-minute

²⁹ Maisano F, Franzen O, Baldus S, Schafer U, Hausleiter J, Butter C, Ussia GP, Sievert H, Richardt G, Widder JD, Moccetti T, Schillinger W. Percutaneous Mitral Valve Interventions in the Real World: Early and 1-Year Results from the ACCESS-EU, a Prospective, Multicenter, Nonrandomized Post-Approval Study of the MitraClip Therapy in Europe. *J Am Coll Cardiol*. 2013; 62:1052-1061.

walk (59.5 m difference, $p < 0.0001$), Minnesota Living with Heart Failure Questionnaire quality of life score (13.5 point improvement, $p < 0.0001$) and NYHA Functional Class (71.5% NYHA Class I or II, $p < 0.0001$), at 1 year, the study is concluded that the MitraClip device provides an important therapeutic option for patients with significant mitral regurgitation, and is an especially important option for patients who may be considered high surgical risk.

The GRASP registry was a single-center, prospective, observational study of consecutive high surgical risk patients with moderate-to-severe or severe MR undergoing percutaneous mitral valve repair with the MitraClip System at Ferrarotto Hospital (Catania, Italy). The study does not have specific exclusion criteria; and the indication for MitraClip therapy was established by a multidisciplinary Heart Team. The degree of preprocedural MR was quantified according to current guidelines by two expert echocardiographers. A total of 117 consecutive patients underwent MitraClip implantation between August 2008 and October 2012 as part of the GRASP registry³⁰. MR grade 3+ or 4+ was present in 98% of patients, and NYHA functional class symptoms in 80% of patients. Acute procedural success was achieved in all patients. MR was reduced to 1+ and 2+ post-procedure in 63% and 37% of patients, respectively. MAEs occurred in 4 patients (4.3%) at 30 days. One patient died from gastrointestinal bleeding within 30 days. Results from the GRASP registry further support the safety and efficacy of the MitraClip device in a real-world setting.

The German transcatheter mitral valve interventions (TRAMI) registry was initiated in August 2010 to collect data from clinical centers in Germany involved in transcatheter therapies for mitral valve disease. The registry comprises a retrospective part, including patients who have been treated at individual sites prior to study initiation, and a prospective part after study site initiation. Follow-up for the retrospective part was not defined in the study protocol and was performed according to institutional practice. Follow-up for the prospective part was scheduled at 30 days and then at 1, 3, and 5 years. Several reports on TRAMI have been published over the years^{31,32}. The largest prospective cohort was described by Puls et al.³³. A total of 828 patients were prospectively enrolled at 21 German sites between 2010 and 2013. One-year follow-up was available in 749 patients. The MitraClip implant rate in this cohort was 97%, with an average of 1.4 ± 0.6 clips implanted per procedure. Mitral regurgitation was reduced from severe (94%) at baseline to none or mild in 85.2% of patients post procedure. One patient died intra-operatively and in-hospital mortality was 2.4% ($n=18$). No emergent cardiac surgery was required. The rate of in-hospital Major adverse cardiac and cerebrovascular events (MACCE) was 3.1%. These results demonstrate that treatment of significant MR with the MitraClip device is efficacious and results in

³⁰ Grasso C, Capodanno D, Scandura S, Cannata S, Imme S, Mangiafico S, Pistrutto A, Ministeri M, Barbanti M, Caggegi A, Chiaranda M, Dipasqua F, Giaquinta S, Occhipinti M, Ussia G, Tamburino C. One- and Twelve-Month Safety and Efficacy Outcomes of Patients Undergoing Edge-to-Edge Percutaneous Mitral Valve Repair (from the GRASP Registry). *Am J Cardiol.* 2013; 111:1482-1487.

³¹ Baldus S, Schillinger W, Franzen O, Bekeredjian R, Sievert H, Schofer J, Kuck KH, Konorza T, Mollmann H, Hehrlein C, Ouarrak T, Senges J, Meinertz T, investigators GTMVI. MitraClip Therapy in Daily Clinical Practice: Initial Results from the German Transcatheter Mitral Valve Interventions (TRAMI) Registry. *Eur J Heart Fail.* 2012; 14:1050-1055.

³² Schillinger W, Hunlich M, Baldus S, Ouarrak T, Boekstegers P, Hink U, Butter C, Bekeredjian R, Plicht B, Sievert H, Schofer J, Senges J, Meinertz T, Hasenfuss G. Acute Outcomes after MitraClip Therapy in Highly Aged Patients: Results from the German Transcatheter Mitral Valve Interventions (TRAMI) Registry. *EuroIntervention.* 2013; 9:84-90.

³³ Puls M, Lubos E, Boekstegers P, von Bardeleben RS, Ouarrak T, Butter C, Zuern CS, Bekeredjian R, Sievert H, Nickenig G, Eggebrecht H, Senges J, Schillinger W. One-Year Outcomes and Predictors of Mortality after MitraClip Therapy in Contemporary Clinical Practice: Results from the German Transcatheter Mitral Valve Interventions Registry. *Eur Heart J.* 2016; 37:703-712.

significant clinical improvements in a high proportion of TRAMI patients after 12 months. In this cohort, failure to achieve procedural success had the highest hazard ratio for predicting 1-year mortality.

The Transcatheter Valve Treatment Sentinel Pilot Registry is part of the European Society of Cardiology EuroObservational Research Programme and reports acute and 12-month follow-up results of 628 consecutive patients treated between January 2011 and December 2012 in 25 centers in 8 European countries. Acute procedural success was high (95.4%) with no difference between FMR and DMR patients. Overall, in-hospital mortality was 2.9%. MR reduction to $\leq 2+$ was achieved in 98.2% of patients post-procedure with no difference between MR etiologies. At 1-year, MR was reduced to $\leq 2+$ in 94.0% of patients and 58.6% had mild or no MR, with comparable results obtained for FMR and DMR. The results of the pilot European Sentinel Registry demonstrated that procedural and late mortality was low and lower than expected in such a high-risk cohort, without differences between FMR and DMR. These results confirm long-term benefits previously reported in other real-world registries.

The totality of post-market clinical evidence supports the use of the MitraClip System for the treatment of MR. The MitraClip XTR PMCF Study will assess the safety and performance of the next generation MitraClip XTR system to confirm that the new design also performs safely and with acceptable outcomes.

2.2 Rationale for Conducting this Study

This Study will meet PMCF requirements to confirm safety and performance of the next generation MitraClip XTR System. The primary analysis will be conducted using the endpoint of Acute Procedural Success (APS). APS is evaluated by taking into account both safety and performance by capturing safety events related to device failure (re-intervention or death) and performance by the assessment of MR (reduced MR to MR $2+$ or less). APS will be evaluated upon discharge from the hospital post procedure. A comparison to the APS rate established by historical clinical data will show the next generation MitraClip XTR System offers the safety and performance expected from MitraClip.

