Title	Post-Market Clinical Follow-up Assessment of the Safety and Performance the MitraClip XTR System
Objectives	The primary objective of this study to evaluate the safety and performance of the MitraClip XTR System in a post-market setting.
Device	MitraClip XTR System
Targeted number of subjects	A minimum of 220 subjects
Subject Follow-up	Clinical Visit: 30 days and 12 Months Phone Call: 6 Months
Primary Endpoint	Safety and Effectiveness Acute Procedural Success (APS) defined as successful implantation of the MitraClip XTR device with resulting MR severity of 2+ or less on discharge Echocardiogram (30-day echocardiogram will be used if discharge is unavailable or uninterpretable). Subjects who die or undergo mitral valve surgery before discharge are considered to be an APS failure
Clinical Endpoints	
 • Major Adverse Event (MAE). MAE defined as a composite of all-cause Death, Myocardial Infarction, Stroke, or non-elective CV surgery for device related complications (CEC adjudicated) • MR Severity • Device Related Adverse Events (including Mitral valve stenosis, device embolization, Single Leaflet Device Attachment (SLDA), iatrogenic atrial septal defect, Myocardial perforation, or the need for mitral valve replacement instead of repair due at least in part to the MitraClip procedure or the presence of the MitraClip device)) • All-cause mortality • Recurrent heart failure hospitalization • New York Heart Association (NYHA) functional class improvement
Inclusion Criteria	
 1. Subjects scheduled to receive the MitraClip per the current approved indications for use 2. Subjects who give consent for their participation 3. Subjects with Symptomatic MR ($\geq 3+$)
Exclusion Criteria	
 1. Subjects participating in another clinical study that could impact the follow-up or results of this study.

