4.0 ENDPOINTS

4.1 Primary Endpoint

The primary endpoint is Acute Procedural Success (APS). This is defined as successful implantation of the MitraClip device with resulting MR severity of 2+ or less upon discharge Echocardiogram (30-day echocardiogram will be used if discharge is unavailable or uninterpretable). Subjects who die or undergo mitral valve surgery before discharge are an APS failure

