4.3 Success Criteria

The MitraClip XTR PMCF Study will be successful if the lower one-sided 95% confidence interval (CI) of the observed APS rate for the study is greater than the Performance Goal (PG) of 80.7%.

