9.2 Analysis Populations

9.3 Sample Size Calculations and Assumptions

The sample size of a minimum 220 subjects is determined based on the endpoint of APS. APS is defined as successful implantation of the MitraClip Implant with resulting MR severity of 2+ or less on discharge Echocardiogram.

The powered endpoint of APS will be evaluated against a pre-specified clinical performance goal (PG). The power calculation is based on the following statistical hypotheses and assumptions:

- H₀: APS rate ≤ PG
- H_A: APS rate > PG

- [REDACTED]
- One-sided type I error rate = 0.05

[REDACTED]

[REDACTED]

The sample size calculation was performed using PASS 15 (Hintze J, 2017, NCSS, LLC. Kaysville, Utah).

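### Passing the PMCF's APS test can support acute procedural performance, but not the safety conclusion that the plan also draws from it

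*Protocol*

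**What the plan says.** All section numbers here refer to the XTR PMCF protocol in Protocol Appendix I unless stated otherwise.

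- The protocol summary puts the primary endpoint under the label "Safety and Effectiveness" and gives one endpoint there: "Acute Procedural Success (APS) defined as successful implantation of the MitraClip XTR device with resulting MR severity of 2+ or less on discharge Echocardiogram".
- Section 4.1 adds the safety element: "Subjects who die or undergo mitral valve surgery before discharge are an APS failure".
- Section 2.2 explains the choice: "APS is evaluated by taking into account both safety and performance by capturing safety events related to device failure (re-intervention or death"). It goes on to say that comparison with the historical APS rate will show that XTR has the safety and performance expected of the device family.
- Section 4.3 gives the only success rule: "The MitraClip XTR PMCF Study will be successful if the lower one-sided 95% confidence interval (CI) of the observed APS rate" "is greater than the Performance Goal (PG) of 80.7"%.
- Section 9.4.3 confirms that there is one primary endpoint. MAE, all-cause mortality and device-related events are clinical endpoints (4.2), and 9.4.2 has them summarised descriptively.

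The SAP describes the parent EXPAND study, states that it has no hypothesis testing (2.9), and adds no safety criterion for the PMCF.

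**The concern.** The plan attaches a safety conclusion to a test that mostly answers another question. A single yes/no outcome cannot tell a death from a residual MR grade of 3+, so good MR results can offset extra deaths. The safety content is also narrow. Stroke and MI do not count in themselves, and neither does a death after discharge. Section 2.2 speaks of re-intervention, but 4.1 counts only mitral valve surgery. No MAE or mortality result can change whether the study is declared successful.

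The PMCF is meant to meet a CE-mark follow-up requirement (1.0). A pass could therefore be reported as formal confirmation of safety when the formal test gives little or no assurance of it.

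**Working it through.** **Inputs.** Minimum n = 220 (9.3). Goal 80.7% (4.3). "One-sided type I error rate = 0.05" (9.3). Exact test (9.4.1). Sentinel registry (2.1): APS 95.4%, MR 2+ or less in 98.2%, and "Overall, in-hospital mortality was 2.9"%. Further baselines come from the main protocol's Appendix IV.

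**Step 1: the plan's own rule.** The one-sided 95% Clopper-Pearson lower limit for x successes is the 5% quantile of a Beta(x, 221 − x) distribution.
- x = 187: 80.46%, fail.
- x = 188: 80.96%, pass.

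The pass mark is 188/220 = 85.45%, with exact size P(X ≥ 188 | 0.807) = 0.041. Tolerated failures: 220 − 188 = 32, or 14.5%. The figure of 220 itself cannot be reproduced, because the expected APS rate and the power are blacked out. Solved backwards, n = 220 gives 80% power at a true APS of 87.1% and 90% power at 88.1%.

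**Step 2: raise in-hospital death from the Sentinel baseline.** Let k multiply in-hospital death and hold MR success among survivors at 98.2%: APS(k) = (1 − 0.029k) × 0.982. At k = 1 this is 0.971 × 0.982 = 0.954, which matches the stated APS.

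| k | In-hospital death | APS(k) | P(X ≥ 188) |
|---|---|---|---|
| 1 | 2.9% | 0.954 | >0.999 |
| 2 | 5.8% | 0.925 | >0.999 |
| 3 | 8.7% | 0.897 | 0.98 |
| 4 | 11.6% | 0.868 | 0.76 |

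Subtracting the extra deaths directly (95.4 − 2.9(k − 1)) gives 0.979 at k = 3 and 0.745 at k = 4.

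**Step 3: change the baseline.** In-hospital death tripled each time, same pass mark.

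| Baseline | APS when tripled | P(pass) |
|---|---|---|
| First TVT report: procedural success 90.6%, death 2.3% | 90.6 − 4.6 = 86.0% | 0.64 (0.69 if scaled proportionally) |
| Later TVT report: MR 2+ or less 93.0%, death 2.7% | (1 − 0.081) × 0.930 = 85.5% | 0.55 |
| REALISM High Risk: MR 2+ or less 90%, death before discharge 1.9% | (1 − 0.057) × 0.90 = 84.9% | 0.45 |
| Assumed APS 90%, death 2.9% | 90 − 5.8 = 84.2% | 0.34 |
| Assumed APS 88%, death 2.9% | 88 − 5.8 = 82.2% | 0.12 |

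The later TVT and REALISM rows treat the reported MR rate as the rate among survivors, which is an assumption. In the first TVT report, doubling (90.6 − 2.3 = 88.3%) passes with probability 0.92.

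**Step 4: where the slack comes from.** Under Sentinel the goal lies 95.4 − 80.7 = 14.7 points below the expected rate, while tripling removes 2 × 2.9 = 5.8 points. With a 90% goal the pass mark would be 206. The Sentinel baseline would then pass with probability about 0.91, doubled death 0.31 and tripled death 0.03.

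**The case against.** The strongest reply is that safety does not rest on APS alone. Section 1.1 has adverse events through 12 months assessed to further confirm safety, 4.2 lists CEC-adjudicated MAE and all-cause mortality, and 9.4 already plans exact Clopper-Pearson intervals for binary outcomes and Kaplan-Meier for mortality. A composite primary endpoint with descriptive safety is an acceptable choice for a single-arm post-market study of an approved device. All of this stands. It means the data for a safety statement will exist; it does not make a pass on APS into one, which is what 2.2 says.

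Four stronger readings are tempting and are not supported:

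- A reader might infer that the test passes 98% of the time under tripled mortality as a fixed property. That figure belongs to the Sentinel baseline. Step 3 shows much lower values, and the sponsor's expected rate cannot be seen. If it lies near 87 to 88%, a tripling would mostly fail.
- A reader might infer that deaths are a minor part of APS failure. Under Sentinel they are 2.9 of 100 − 95.4 = 4.6 points, about 63%. In the first TVT report they are 2.3 of 9.4 points, about 24%.
- A reader might infer that the insensitivity would arise at any goal. Step 4 shows that a 90% goal would usually catch a tripling.
- A reader might infer that 32 deaths would plausibly be accepted. That is the ceiling of the rule and needs no residual MR failures at all.

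**Conclusion.** The concern holds as a mismatch between the test and the claim. Meeting the APS goal does not by itself support the safety conclusion in 2.2 and the summary, because the outcome is pooled, its safety content stops at death or mitral surgery before discharge, and no safety endpoint has its own criterion. How much excess mortality the test would miss depends on the baseline: for tripled in-hospital death, about 0.98 under Sentinel and 0.45 to 0.69 under other figures in the protocol. The cause is the pooling together with the distance between the goal and the true APS rate.

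This rests on n = 220 exactly, the one-sided exact test, independent outcomes, and extra deaths falling on patients who would otherwise mostly have been successes. The blacked-out text in 9.3 and 9.4.1 cannot be checked, but 4.3, 9.4.2 and 9.4.3 leave no visible place for a second criterion. The point is worth correcting because it changes what the study may claim. It does not invalidate the APS test as a test of performance.

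**What to change.** In section 2.2, section 4.3 and the summary label, state that meeting the APS goal supports acute procedural performance only. Align the mention of re-intervention in 2.2 with the mitral surgery wording in 4.1.

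In 9.4.2, base any safety statement on three separate lines: in-hospital death, mitral valve surgery before discharge, and CEC-adjudicated 30-day MAE. Give each an exact one-sided 95% upper limit, set beside the historical rates already cited, with a note wherever the historical MAE definition is broader than the PMCF's.

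Such limits would be informative at this size. The upper limit for x events is the 95% quantile of Beta(x + 1, 220 − x). Six deaths (0.029 × 220 = 6.4) give 5.3%; 19 deaths (0.087 × 220 = 19.1) give 12.4%.

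A formal MAE goal is optional. It would need its own justified number and power, which the documents do not supply.

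The cost is wording in the PMCF protocol and its analysis plan. The events are already collected, and MAE is already adjudicated. The downside is a narrower success statement.

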2.3 Summary of Device

2.3.1 Name of the Device

Patients will be treated with MitraClip XTR System as part of this study after all required commercial approval for the device is obtained.

2.3.2 Indication for Use

MitraClip XTR procedures for this study will be conducted in accordance with the Instructions for Use (IFU) that is approved for the region, where the implant is taking place.

2.3.3 Description of the Device

The MitraClip System is intended for reconstruction of the insufficient mitral valve through tissue approximation. The MitraClip System comprises of the Clip Delivery System and Steerable Guide Catheter. The Clip Delivery System is introduced into the body through the Steerable Guide Catheter.

The MitraClip XTR System is an additional implant size to be used with a modified Delivery Catheter. The additional implant size is intended to assist clinicians with leaflet grasping. The modified delivery catheter is designed to make the procedure more precise, more predictable, and to optimize manufacturability of the product.

3.0 FOLLOW-UP SCHEDULE

[figure not shown]
3.1 Number of Subjects to be Enrolled

Subjects who have provided written informed consent are considered enrolled. Upon treatment with MitraClip XTR the subject will be included in this PMCF analysis. A minimum of 220 commercial MitraClip XTR patients will be analyzed at a maximum of 50 centers in the EU as part of this PMCF study.

3.2 Overall Flow of the Study and Follow-up Schedule

Consecutive eligible patients that present for MitraClip procedure should be consented for the MitraClip XTR PMCF Study. Patients are included in the analysis upon completion of MitraClip XTR procedure. A schematic of the study flow for the study is shown in **Figure 1**.

Figure 1: Schematic for Study Inclusion

3.3 Early Termination of the Clinical Study

No formal statistical rule for early termination of the MitraClip XTR PMCF Study is defined. The Sponsor reserves the right to discontinue the study at any stage or reduce the follow up period with suitable written notice to the investigator. Possible reason(s) may include, but are not limited to:

- Unanticipated adverse device effect (UADE) occurs and it presents an unreasonable risk to the participating subjects.
- Further product development is cancelled.

Should the study be discontinued by the Sponsor, patients will be followed up as per routine hospital practice with device related AEs being reported to the Sponsor as per vigilance/commercial reporting requirements. Should this occur, the investigator shall return all clinical study materials to the Sponsor, and provide a written statement as to why the premature termination has taken place to the EC.

